### 3.2.11.2 Physical and Mental Component Scores

Following the transformation of the eight domain scores into z-scores, the Mental Component Summary (MCS) and the Physical Component Summary (PCS) are aggregated using weights from the 1990 US general population:

$$AGG\_PHYS = (PF\_Z * 0.42402) + (RPh\_Z * 0.35119) + (BP\_Z * 0.31754) + (GH\_Z * 0.24954) + (VT\_Z * 0.02877) + (SF\_Z * -0.00753) + (RE\_Z * -0.19206) + (MH\_Z * -0.22069)$$

$$\text{AGG\_MENT} = (\text{PF\_Z} * -0.22999) + (\text{RPh\_Z} * -0.12329) + (\text{BP\_Z} * -0.09731) + (\text{GH\_Z} * -0.01571) + (\text{VT\_Z} * 0.23534) + (\text{SF\_Z} * 0.26876) + (\text{RE\_Z} * 0.43407) + (\text{MH\_Z} * 0.48581)$$

Finally, each component score is transformed to norm-based scoring using the following formulas:

Transformed Physical Score: PCS = 50 + (AGG\_PHYS \* 10)

Transformed Mental Score: MCS = 50 + (AGG\_MENT \* 10)

Component scale scores (PCS and MCS) will be set to missing if the subject is missing any one of the eight SF-36 scales.

While the norm-based scores are calculated such that the mean  $\pm$  SD of these scores in the US general population is  $50 \pm 10$ , the lowest and highest possible scores for the PCS are 1 and 81, respectively. For the MCS, the lowest and highest possible scores are -9 and 82, respectively.

### 3.2.12 FACIT-Fatigue

The Functional Assessment of Chronic Illness Therapy (FACIT) -fatigue questionnaire is a patient-reported measure developed to assess fatigue consisting of 13 statements regarding feeling fatigue using a numeric rating scale (NRS) ranging from 0 to 4. For only two of the items (i.e. An5 and An7) a higher value represents a lower fatigue; 11 of the item scores (i.e. HI7, HI12, An1, An2, An3, An4, An8, An12, An14, An15, An16) have to be reversed by subtracting the captured value from 4 (0 is turned to a 4; 1 into 3; 3 into 1; 4 into 0).

After performing the reversals the sum of the non-missing individual items will be multiplied by 13 and divided by the number of the non-missing individual items.

The final score ranges from 0 to 52 with higher values representing a lower fatigue (i.e. a better quality of life).

If more than 6 individual items are missing at an assessment the FACIT-Fatigue score will be set to missing at that assessment.

### 3.2.13 BFI

Brief Fatigue Inventory (BFI) is a self-reported instrument consisting of nine questions which correlate well with quality-of-life measures. For this study, Question 3 only will be used which asks about fatigue severity at its worst in the last 24 hours.

A discrete 11 unit NRS will be used where 0 is “No fatigue”, and 10 is “As bad as you can imagine”.

No imputations will be done for missing data.

### 3.2.14 Borg Dyspnea Scale

The Borg dyspnea scale will be used to assess dyspnea. A discrete 18 unit scale will be used ranging from “Nothing at all” to “Absolute maximum”.

No imputations will be done for missing data.

## 4 STATISTICAL METHODS

### 4.1 Data Quality Assurance

All tables, figures and data listings to be included in the report will be independently checked for consistency, integrity and in accordance with standard PAREXEL procedures.

### 4.2 General Presentation Considerations

For each subject 'Baseline' is defined as the last available assessment prior to the start of study treatment. For Efficacy variables no Screening information will be used for Baseline. For DLCO, separate Baseline rules are defined in section 4.10.9. For each subject 'End of Study' is defined as the last available assessment which is on or after the day of last study treatment.

The relative study day will be included in adverse event data, medical history and concomitant medication listings, and will be calculated as follows:

- Relative Day 1 is the date of first study medication administration.
- Relative Day of date X = date X - Date of first study medication administration + 1 if date X is on or after date of first study medication administration.
- Relative Day of date X = date X - Date of first study medication administration if date X is before date of first study medication administration.

Relative days before first study medication administration will have the prefix “-“. Additionally for relative days after last study medication administration, the number of days since last study medication administration will be presented with the prefix “+“. Calculations of “Relative Day” will not include partial dates, but will be left blank in listings.

According to the design the study can be split into 5 time periods:

- Baseline to <Week 14: Day of first study medication administration up to and including the day before Week 14 study medication administration
- Week 14 to <Week 26 visit
- Week 26 to <Week 38 visit
- Week 38 to <Week 52 visit
- Safety Period: Week 52 visit to end of study

Safety period includes Week 52 and all later visits. All other periods start with (and include) Baseline visit or Week 14/26/38 visit and end with the day before the next period starts. Start of a new period is always the day of study medication administration. Safety Period starts with the Week 52 Visit. If the Week 52 visit is missing, Safety Period starts 14 days after the last study drug administration of the previous period.

If the Week 14/26/38 visit is missing, the day of the next non-missing visit will be the first day of the new period. For example, if the Week 14 visit was missed but the Week 16 visit was

conducted, the first time period will end the day prior to the Week 16 visit. This ensures that all Adverse Events (AEs) reported during the initial treatment period are attributed to the initial dose. If no end date for a period can be identified with the above rules, then the period ends 13 days after the last day of study drug administration of that period.

Continuous data will be summarised in terms of the mean, SD, median, minimum, maximum and number of observations, unless otherwise stated. The minimum and maximum will be reported to the same number of decimal places as the raw data recorded in the database. The mean, median, lower quartile and upper quartile will be reported to one more decimal place than the raw data recorded in the database. The SD will be reported to two more decimal places than the raw data recorded in the database. In general, the maximum number of decimal places reported shall be four for any summary statistic.

Categorical data will be summarised in terms of the number of subjects providing data at the relevant time point (n), frequency counts and percentages.

If not stated otherwise percentages will be presented with one decimal place. Percentages will not be presented for zero counts. Percentages will be calculated using n as the denominator. 100% will be presented without decimal places.

P-values greater than or equal to 0.001, in general, will be presented to three decimal places. P-values less than 0.001 will be presented as “<0.001”.

Confidence intervals (CI) will be presented to one more decimal place than the raw data.

All report outputs will be produced using SAS® version 9.2 or a later version in a secure and validated environment. Tables, listings and figures will each be provided in a separate rtf document as well as in a separate pdf documents.

### 4.3 Analysis Populations

**Screened Population:** The SP will consist of all subjects who got screened.

**Randomised Population (RP):** The RP will consist of all subjects who were randomised to treatment.

**Intent-to-Treat (ITT) Population:** The ITT population will consist of all subjects who were randomised to treatment and who received at least one dose of study treatment (GSK3196165 or placebo).

**Pharmacokinetic (PK) Population:** The PK population will consist of all subjects in the ITT population, who had at least one valid pharmacokinetic assessment.

**Immunogenicity Population:** The immunogenicity population will consist of all subjects in the ITT population, who had at least one valid immunogenicity assessment.

**Actigraphy Population (AP):** The AP will consist of all subjects in the ITT population who consent to participate in the actigraphy substudy.

**Genetic Research Population (GRP):** The GRP will consist of all subjects in the ITT population who consent to participate in the genetic research. Any subject who has received an allogeneic bone marrow transplant must be excluded from the genetic research.

All endpoints will be analysed for the ITT population by randomised treatment group. Numbers and percentages of subjects in each analysis population will be summarised by randomised treatment group. Subjects who received at least one wrong dose will be presented in a listing. Additional summaries may be provided if considered necessary.

A by-subject listing of analysis population details will be provided. This listing will be presented by randomised treatment group and will include: center, subject identifier, inclusion/exclusion flag for each population and reason for exclusion from each population. All subjects screened will appear on this listing.

#### 4.3.1 Analysis Datasets

For each of the efficacy evaluations of binary endpoints, subjects with missing efficacy data, early withdrawals, subjects who received more than 10 mg/day of prednisone equivalent oral corticosteroids, subjects with any new use of parenteral corticosteroids, more than one intra-articular corticosteroid injection within a 24 week period, or subjects who received rescue treatment will be imputed as non-responders and therefore treated as a failure (e.g. no DAS28(CRP) remission or no moderate/good EULAR response). Imputation rules for each case are described in section 4.5.2:

A dataset will be created with these imputation rules and will be referred to as the NRI dataset. The NRI dataset will be the primary dataset used for all binary efficacy endpoints. Imputed response for each binary endpoint will be presented by visit and subject in listings.

For the efficacy evaluations of continuous endpoints, results recorded for subjects who received rescue treatment or exceeded 10 mg/day prednisone equivalent oral corticosteroids, subjects with any new use of parenteral corticosteroids, more than one intra-articular corticosteroid injection within a 24 week period, or subjects who received rescue treatment will be set to missing at the same visits that were set to non-responder for the binary endpoints. This is a change from protocol section 9.3.2. A dataset will be created and will be referred to as the Set-to-Missing (STM) dataset.

For safety endpoints, no imputation for missing data will be done.

### 4.4 Study Subjects

#### 4.4.1 Disposition of Subjects

A clear accounting of the disposition of all subjects who enter the study will be provided, from screening to study completion.

The following subject disposition summaries will be provided: See Section 4.3 for a description of the analysis populations.

A summary of the number of subjects who were screened for entry into the study and

- were excluded prior to randomisation by major reason and overall (Analysis population: All Subjects Screened)
- were randomised per center, per country, and by disease duration (<2 years, ≥2 years) and randomised treatment group (Analysis population: Randomised Population)
- received at least one dose of study medication by randomised treatment group (Analysis population: Randomised Population)
- withdrew from the study by major reason by randomised treatment group (Analysis population: ITT Population)
- completed the study by randomised treatment group (Analysis population: ITT Population)
- completed 12/24/36/50 weeks of treatment by randomised treatment group (Analysis population: ITT Population)
- completed 12/24/36/50 weeks of treatment without dose escalation by randomised treatment group (Analysis population: ITT Population)
- were escalated to highest dose at Week 14/26 by randomised treatment group (Analysis population: ITT Population)
- were escalated to highest dose at Week 14/26 and completed 24/36/52 weeks of treatment by randomised treatment group (Analysis population: ITT Population)
- were withdrawn from study at Week 38 due to lack of EULAR good/moderate response by randomised treatment group (Analysis population: ITT Population)

By-subject listings of eligibility details, randomisation details by site (including subject id, randomisation number and randomised treatment group and information whether the blind was broken at discontinuation), visit dates (including actual treatment received at each visit) and withdrawal/study completion details (including reason for discontinuation and duration of treatment prior to discontinuation) will be provided.

#### 4.4.2 Protocol Deviations

Protocol deviations (PDs) will be managed and reported according to PAREXEL Standard Operating Procedures (SOPs).

Details will be given in the Protocol Deviation Specification (PDS) document, which will include detailed information regarding definitions, classifications, tracking and management of PDs.

PDs will be categorised as major or minor as further described in the PDS.

PDs will also be classified into the following categories: Informed Consent, Inclusion/Exclusion Criteria, Withdrawal Criteria, IP Admin/Study Treat, Disallowed Medications, AE/SAE, Visit Schedule, Procedures/Tests, Other.

Observable PDs that can only be identified by project team members during the monitoring, but cannot be programmed, will be tracked and reconciled with programmable (data driven) PDs, that can be programmed from the recorded data.

A combined PD dataset will include all PDs.

Special considerations are needed for (potentially) unblinding PDs, which will be handled in separate unblinded areas with restricted access.

Summaries of the number and percentage of subjects with a major/minor protocol deviation will be provided by randomised treatment group and by type of deviation (Analysis population: Randomised Population).

A by-subject listing of all protocol deviations will be provided.

## 4.5 General Data Handling Conventions

### 4.5.1 Missing Dates

In analysis of AEs and medication a complete date will be established in order to identify AEs or medication as occurring during treatment or not. For handling partially reported onset/start and outcome/end dates for AEs or medication the following algorithms are applied:

- AEs:
  - Missing onset day, but month and year present:  
If study medication had been taken in the same month and year as the occurrence of the AE, then the onset day of the event is assigned to the day of first dose of study medication.  
Otherwise the onset day is set to the first day of the month (eg, XX-Sep-2010 is considered as 01-Sep-2010).
  - Missing onset day and month, but year present:  
If study medication had been taken in the same year as the occurrence of the AE, then the onset date of the event is assigned to the date of first dose of study medication.  
Otherwise the onset day and month is set to 01 January (eg, XX-XXX-2010 is considered as 01-Jan-2010).
  - Missing outcome day, but month and year present:  
The day is set to the last day of the month (eg, XX-Sep-2010 is considered as 30-Sep-2010).
  - Missing outcome day and month, but year present:  
The outcome day and month is set to 31 December (eg, XX-XXX-2010 is considered as 31-Dec-2010).
- Medications:
  - Missing start day, but month and year present:  
If first study medication administration had been taken place in the same month and year as the occurrence of the medication, then the start day of the medication is assigned

to the day of first study medication administration. Otherwise the start day is set to the first day of the month (eg, XX-Sep-2010 is considered as 01-Sep-2010).

- Missing start day and month, but year present:  
If first study medication administration had been taken in the same year as the occurrence of the medication, then the start date of the medication is assigned to the date of first study medication administration.
- Otherwise the start day and month is set to 01 January (eg, XX-XXX-2010 is considered as 01-Jan-2010).
- Missing stop day, but month and year present:  
The day is set to the last day of the month (eg, XX-Sep-2010 is considered as 30-Sep-2010).
- Missing stop day and month, but year present:  
The stop day and month is set to 31 December (eg, XX-XXX-2010 is considered as 31-Dec-2010).
- RA diagnosis and symptom onset:
  - Missing day, but month and year present:  
Date is set to the first day of the month (eg, XX-Sep-2010 is considered as 01-Sep-2010).
  - Missing day and month, but year present:  
Date is set to 01 January (eg, XX-XXX-2010 is considered as 01-Jan-2010)
- End date of Tobacco use:
  - Missing outcome day, but month and year present:  
The day is set to the last day of the month (eg, XX-Sep-2010 is considered as 30-Sep-2010).
  - Missing outcome day and month, but year present:  
The outcome day and month is set to 31 December (eg, XX-XXX-2010 is considered as 31-Dec-2010).

In data listings, onset/start and outcome/stop date of AEs, medication, diagnosis, or symptoms is displayed as reported.

## 4.5.2 Missing Data for Efficacy and Safety Endpoints

### 4.5.2.1 Missing Data for Efficacy Endpoints

Missing visit data for each efficacy endpoint will be handled as described in Sections 3.2 and 4.3.1. For each continuous endpoint, change from baseline will be missing at visits with missing post-baseline values or where data were imputed to missing.

For the binary endpoints, subjects with missing efficacy data, early withdrawals, subjects who exceed the allowed dose of corticosteroid, who received new parenteral corticosteroids or more than one intra-articular corticosteroid injection within a 24 week period, or subjects who received rescue treatment will be imputed as non-responders and therefore treated as a failure (e.g. no DAS28(CRP) remission or no moderate/good EULAR response).

For subjects who exceed the allowed dose of corticosteroid, who received new parenteral corticosteroids or more than one intra-articular corticosteroid injection within 24 weeks or subjects who received rescue treatment, continuous efficacy endpoints will be set to missing.

- Missing efficacy data: visits with missing data (due to a missed visit or missing component of a composite endpoint) should be set to treatment failure.
- Early withdrawals (including subjects that are withdrawn at Week 36 due to lack of EULAR response): only visits following the early withdrawal visit should be set to treatment failure.
- Prednisone equivalent >10 mg/day: the visit after a period (time from previous visit up to the day before the current visit) of average daily corticosteroid use exceeding 10 mg/day prednisone and all following visits should be set to treatment failure (continuous endpoints will be set to missing).
- Parenteral corticosteroids: all visits after a subject received any new parenteral corticosteroids (e.g. intravenous and intra-muscular) should be set to treatment failure (continuous endpoints will be set to missing).
- Intra-articular corticosteroids: all visits after the second intra-articular corticosteroid injection within a 24 week period should be set to treatment failure (continuous endpoints will be set to missing).
- Rescue: subjects who rescue to 180 mg dose at Week 14 or 26 should be set to treatment failure at that visit and all subsequent visits (continuous endpoints will be set to missing).

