### **6.11.1.1. Corticosteroids**

#### **6.11.1.1.1. Oral Corticosteroids**

Stable use of oral corticosteroids  $\leq$ 10 mg/day prednisone or equivalent agent is permitted if the dose is stable for at least 28 days prior to Day 1 (baseline). This dose should remain constant throughout the first 12 weeks of the study. Dose reductions before Week 12 are not permitted, unless required for safety or tolerability.

If the corticosteroid dose is increased above 10 mg/day prednisone, the subject will be deemed a treatment failure and investigational product will be discontinued, although the subject will remain on study and undergo study visits as outlined in the Time and Event Table Section 7.1.

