##### 9.2.1.1. Primary Analysis

The sample size for the primary analysis and hence the overall sample size for the study is based on detecting a 30% difference from placebo in the proportion of subjects in remission (DAS28 score <2.6) at Week 24 of the 52 week double-blind treatment period for each GSK3196165 dose.

Using a Fisher's exact test, a sample size of 35 subjects per arm will provide approximately 90% power to detect a difference of 30% in the proportion of subjects in remission between each GSK3196165 dose (33%) and placebo (3%) at the two-sided  $\alpha=0.05$  level at 24 weeks. The placebo rate of 3% is based on a literature review of current therapies presenting DAS28(CRP) remission results. No adjustments will be made to the sample size to account for the multiple doses in this Phase 2 study.

The least significant difference this sample size will detect is a 17% difference from placebo.

The sample size will not be increased to account for dropouts and all dropouts within the treatment period will be classed as non-remitters for the primary analysis.

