### 9.3.2. Analysis Data Sets

For the binary endpoints (e.g. proportion of subjects achieving remission at 24 weeks), subjects with missing efficacy data (caused by prematurely discontinued subjects or otherwise) or subjects who received rescue treatment will be imputed as non-responders. A dataset will be created with this imputation and will be referred to as Non-Responder Imputation (NRI) and will be the primary dataset used for all binary endpoints.

In addition to the Non-Responder Imputation dataset for binary endpoints, for all efficacy endpoints a Observed Case (OC) dataset will be created, whereby the data are as collected or observed in the study and no imputation is made for missing data. All continuous endpoints will be analysed using the OC dataset and all data will be listed using the (OC) dataset.

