### **9.4.1. Primary Analyses**

The primary efficacy endpoint is the proportion of subjects achieving DAS28(CRP) remission at Week 24 of the 52-week double-blind treatment period in the ITT population using NRI. DAS28(CRP) remission is defined as a DAS28 score of <2.6 points. The DAS28(CRP) score is calculated using the following formula, where TJC = tender joint count, SJC = swollen joint count and PtGA = Patient's Global Assessment of Arthritis:

$$\text{DAS28(CRP)} = 0.56(\sqrt{\text{TJC28}}) + 0.28(\sqrt{\text{SJC28}}) + 0.36(\ln(\text{CRP} + 1)) + (0.014 * \text{PtGA}) + 0.96$$

Subjects with missing DAS28(CRP) scores at Week 24 will be considered as non-remitters. The proportion of subjects in DAS28(CRP) remission will be summarised using counts and proportions in remission and analyzed using a logistic regression analysis adjusted for treatment group and baseline DAS28(CRP) score and will be used to test the treatment comparison of each GSK3196165 dose group versus placebo. For each treatment comparison, an estimate of the odds ratio of achieving remission and the corresponding p-value and 95% confidence interval will be summarised.

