#### **4.5.3 Multiple Assessments and Early Withdrawal Visits**

If a variable has been assessed multiple times at the same visit, only the last assessment will be used except for Electrocardiograms (ECGs) or laboratory measurements. Triplicate ECG measures will be averaged for each subject and visit prior to generating summary tables.

For laboratory values the value with the worst CTCAE grade will be considered. If there is more than one value of this grade, the later value will be considered.

Only scheduled visits will be included in summaries. Listings will include scheduled and unscheduled visits.

Early Withdrawal (EW) visits will be assigned to the respective visit according to the Time and Events table in Section 7.1 of the protocol using the day of the EW visit relative to Day 1. For the first 4 weeks an EW visit more than  $\pm 3$  days in comparison to the target visit will be assigned to the closest target visit. Starting with Week 4, an EW visit more than 7 days after a target visit day will be assigned to the next visit.

If a scheduled visit and an EW visit occur within the same visit window and are both available, the later visit will be used for analyses. The earlier visit will appear in listing only. For efficacy analyses, if an EW visit is assigned to a non-standard efficacy visit, i.e., a visit at which efficacy assessments are not scheduled per the Time and Events Table, then these EW data will be ignored in the statistical analysis.

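### Two SAP rules can misclassify Week 24 remission (a late early-withdrawal visit replaces an attended score; short steroid courses above 10 mg/day pass), and prohibited DMARDs need naming; the expected effect is small

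*SAP*

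**What the plan says.** **Dropouts.** Protocol 9.2.1.1, repeated in SAP 4.13.1, states that "all dropouts within the treatment period will be classed as non-remitters for the primary analysis". The analysis sections are narrower. Under Protocol 9.3.2, "subjects with missing efficacy data (caused by prematurely discontinued subjects or otherwise) or subjects who received rescue treatment will be imputed as non-responders", and under Protocol 9.4.1, "Subjects with missing DAS28(CRP) scores at Week 24 will be considered as non-remitters". SAP 4.5.2.1 then says of early withdrawals that "only visits following the early withdrawal visit should be set to treatment failure".

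**EW visit mapping.** SAP 4.5.3: "Starting with Week 4, an EW visit more than 7 days after a target visit day will be assigned to the next visit". Where a scheduled visit and an EW visit share a window and "are both available, the later visit will be used for analyses", the earlier one appears only in a listing.

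**Oral steroids.** Protocol 6.11.1.1.1 says that if the dose is raised above 10 mg/day prednisone, "the subject will be deemed a treatment failure and investigational product will be discontinued, although the subject will remain on study". SAP 4.3.1 lists as non-responders "subjects who received more than 10 mg/day of prednisone equivalent oral corticosteroids" and refers to 4.5.2 for the detailed rules. There, the trigger is an average daily dose above 10 mg/day over the period since the previous visit.

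**DMARDs and biologics.** Protocol 6.11.3.1 prohibits conventional DMARDs other than MTX, and all biologics. The lead text of SAP 4.3.1 and 4.5.2.1 fails subjects who received rescue treatment, but the only rescue bullet in 4.5.2.1 is escalation to 180 mg. SAP 4.4.2 mentions disallowed medications only as a protocol deviation category.

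**The concern.** These rules decide who counts as a remitter on the primary endpoint. Read together, they allow three things.

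- A subject who attends Week 24 and withdraws within the following week has the planned primary measurement replaced by a later one.
- A subject whom the protocol deems a treatment failure for steroid use can be scored as a Week 24 remitter, because a short course is averaged away. SAP 4.14 does not list averaging as a change from the protocol.
- A subject who starts a prohibited DMARD or biologic and stays in visits is not explicitly failed.

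The all-dropouts sentence gives a further, different answer for the same subjects. If the conflict remains, somebody has to choose between the rules during programming, possibly after unblinding. With 35 per arm, one reclassified subject moves an arm's remission rate by 1/35 = 2.9 percentage points.

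**Working it through.** **1. The plan's power figure.** Inputs from SAP 4.13.1: 35 per arm, 33% versus 3%, Fisher's exact test, two-sided 0.05. Exact enumeration of the two binomial arms gives 90.9%, against a stated value of approximately 90%. It reproduces.

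**2. Which EW visits become Week 24.** From the Time and Events Table, Week 22 is Day 155 and Week 24 is Day 169.

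- First day mapped forward from Week 22: 155 + 8 = Day 163.
- Last day kept at Week 24: 169 + 7 = Day 176.

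EW visits on Days 163 to 176 are therefore Week 24. With a Week 24 visit attended on Day 169, an EW visit on Days 170 to 176 is the later one and is used. SAP 4.5.2.1 does not fail it, because only visits after the EW visit fail.

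**3. Steroid averaging.** Visits around Week 24 are 14 days apart. For *k* days at 20 mg/day on a background of *b* mg/day, the average is (20*k* + *b*(14 − *k*))/14. The visit fails only if this exceeds 10.

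| Background (mg/day) | Longest course that passes | Average | One day longer | Average |
|---|---|---|---|---|
| 0 | 7 days | 140/14 = 10.0 | 8 days | 160/14 = 11.4 |
| 5 | 4 days | (80 + 50)/14 = 9.3 | 5 days | (100 + 45)/14 = 10.4 |
| 7.5 | 2 days | (40 + 90)/14 = 9.3 | 3 days | (60 + 82.5)/14 = 10.2 |
| 10 | none | – | 1 day | (20 + 130)/14 = 10.7 |

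Every course in the second column is an increase above 10 mg/day under Protocol 6.11.1.1.1. A 10-day course at 20 mg/day from no steroid, split evenly across a visit, averages 100/14 = 7.1 in each interval and passes both. The averaging period is also defined in two ways: SAP 4.5.2.1 stops the day before the current visit, and SAP 4.5.4 includes that visit.

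**4. The all-dropouts sentence.** The treatment period runs up to 52 weeks (Protocol 4.1). Read literally, the sentence fails a Week 24 remitter who leaves at Week 40, which no operative rule does. Even if limited to dropouts before Week 24, it conflicts with scoring EW visits on Days 163 to 168 as Week 24.

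The documents give no withdrawal count, so I assume 10, 20 or 30% dropout spread evenly over 168 days, the EW visit on the day of dropout, and the design remission rate of 33%.

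- Share of subjects: 6/168 × 10/20/30% = 0.36/0.71/1.07%.
- Of 210 subjects: 0.75/1.5/2.25.
- Remitters per active arm: share × 35 × 0.33 = 0.04/0.08/0.12.
- Power with both rates reduced by that share: 90.7/90.6/90.4%.

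This is the gap between the two readings for those six days only. A lower remission rate among withdrawers would shrink it.

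**The case against.** **EW visits.** SAP 4.5.3 is an explicit, prespecified windowing rule, and the all-dropouts sentence sits in the sample-size sections, while Protocol 9.3.2 and 9.4.1 and SAP 4.5.2.1 govern the analysis. That is fair: the EW rule is not an omission, and the dropout sentence needs only editing. It does not explain why a score taken after Week 24 should displace one taken on schedule.

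**Steroids.** SAP 4.3.1 delegates to 4.5.2, so the two SAP sections can be read consistently. The protocol also stops study drug in these subjects, and footnote 1 of the Time and Events Table and SAP 3.1.1 both say that subjects who stop should have an EW visit, after which all visits fail. This narrows the gap considerably. It does not close it: the safeguard works only if the EW visit takes place, and Protocol 6.11.1.1.1 keeps these subjects in scheduled visits.

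**DMARDs.** A reader might infer that the protocol foresees no rescue other than 180 mg, and so that subjects on a new biologic will be counted as remitters. The documents do not support that. Protocol 6.11.2, headed DMARD/Biologic Rescue Medications, also allows for a change in therapy after an excessive flare. A subject who stops study drug for that reason is directed to an EW visit, and the SAP's general wording on rescue treatment may already be meant to cover DMARDs. The protocol deviation specification is not available to check. What remains is a missing explicit bullet.

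**Conclusion.** The point holds at minor severity. Two stated rules, EW replacement and steroid averaging, can misclassify the Week 24 endpoint. The DMARD rule needs to be explicit, and the all-dropouts sentence needs to match the operative rules.

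Three stronger readings are tempting and are not supported:

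- **Bias towards the drug.** The replacement score can be better or worse than the Week 24 score, so no direction is claimed.
- **Overstated power.** The stated figure reproduces. The one part that can be sized, EW visits on Days 163 to 168, lowers it by at most about half a point under the assumptions above (90.9% to 90.4%).
- **All short steroid courses escape.** The gap is widest with no or low background steroid and absent at 10 mg/day.

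Replacements on Days 170 to 176 and steroid and DMARD cases cannot be counted from the documents. I expect few, since each needs an unusual sequence of events. The case for acting is that the rules conflict on the primary endpoint and cost almost nothing to settle.

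**What to change.** 1. **SAP 4.5.3:** when a scheduled Week 24 assessment exists, use it; a later EW visit never replaces it.
2. **SAP 4.5.2.1, oral steroids:** set to failure all visits after the first day on which the oral dose is increased above 10 mg/day prednisone equivalent (continuous endpoints to missing), whether or not study drug was stopped. Alternatively, keep the averaging rule, record it in SAP 4.14 as a change from the protocol, and run the protocol rule as a sensitivity analysis.
3. **SAP 4.5.2.1, rescue bullet:** state that starting a prohibited DMARD or biologic counts as rescue treatment, with failure at all later visits.
4. **SAP 4.13.1:** reword the all-dropouts sentence to match 4.5.2.1 and 4.5.3.

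The cost is SAP wording and minor programming on visit and medication dates that the study already collects, done before the Week 24 unblinding. The downside is that remission counts may be slightly lower.
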